3.5 Adverse Events

3.3.1 Lenalidomide

Most frequently reported adverse events reported during clinical studies with lenalidomide in oncologic and non-oncologic indications, regardless of presumed relationship to study medication include: anemia, neutropenia, thrombocytopenia and pancytopenia, abdominal pain, nausea, vomiting and diarrhea, dehydration, rash, itching, infections, sepsis, pneumonia, UTI, Upper respiratory infection, cellulites, atrial fibrillation, congestive heart failure, myocardial infarction, chest pain, weakness, hypotension, hypercalcemia, hyperglycemia, back pain, bone pain, generalized pain, dizziness, mental status changes, syncope, renal failure, dyspnea, pleural effusion, pulmonary embolism, deep vein thrombosis, CVA, convulsions, dizziness, spinal cord compression, syncope, disease progression, death not specified and fractures.

Complete and updated adverse events are available in the Investigational Drug Brochure and the IND Safety Letters.

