5.7.2 Instructions for initiation of a New Cycle

A new course of treatment may begin on the scheduled Day 1 of a new cycle if::

- The ANC is $\geq 1500/\text{mm}^3$;
- The platelet count is $100,000 \geq /\text{mm}^3$; (If held during the previous cycle for low platelet count, prophylactic anti-coagulation should be re-started when platelet count is $\geq 75,000$)
- Any drug-related rash or neuropathy that may have occurred has resolved to \leq grade 1 severity;
- Any other drug-related adverse events that may have occurred have resolved to \leq grade 2 severity.

If these conditions are not met on Day 1 of a new cycle, the subject will be evaluated weekly and a new cycle of treatment will not be initiated until the toxicity has resolved as described above. If a lenalidomide or everolimus dose reduction was taken during the previous cycle, and the cycle was completed without requiring further dose modification, then the next cycle will start at the same reduced dose. **If drug dosing was omitted for the remainder of the previous cycle or if the new cycle is delayed due to toxicity newly encountered on the scheduled Day 1**, then the

new cycle will be started with a one-level dose reduction of the drug to which the toxicity was attributed.

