5.7.3 Instructions for dose modifications or interruption during a cycle

This information is meant to assist in dose modification for individual study participant who experienced a treatment-related toxicity. The dose escalation schema for the study cohort will proceed as described under the escalation schema (refer Table 1, Section 5.1).

In the event of treatment interruption due to study-drug related toxicity, both agents will be held until the patient is able to resume further therapy. At the time of dosing resumption, alternate dose reduction strategy will be employed if the dose reduction is necessitated by hematologic toxicity. This alternate dose reduction will always start with Lenalidomide (not required if already at the minimum dose of 5mg) followed by Everolimus if further reduction is still necessary. In the case of non-hematological toxicity, dose reduction will be limited to the drug with the highest likelihood of attribution. In case of equal likelihood of attribution or where clear attribution is impossible, simultaneous reduction of both drugs will be effected at resumption of therapy.

NB: Patients unable to resume treatment within the allotted time period for recovery from treatment-related toxicities detailed in Table 5 and Table 6 may be allowed to resume treatment with express approval of the study sponsor provided they have evidence of clinical benefit from treatment and the toxicity has resolved to a level considered safe for further treatment with everolimus or lenalidomide. Also, patient may be allowed to continue on only one study drug if a permanent discontinuation of the other study drug is mandated by a unique treatment-related toxicity e.g. discontinuation of lenalidomide for desquamating rash.

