Platelet count $<$ 50,000/mm³	
 • Hold prophylactic anti-coagulation, if applicable. • Restart prophylactic anti-coagulation when platelet count is \geq 75,000/mm³.
Non-blistering rash Grade 3 Grade 4	
 • If Grade 3, hold (interrupt) lenalidomide dose. Follow weekly. • If the toxicity resolves to \leq grade 1 prior to Day 28, restart lenalidomide at next lower dose level and continue through the scheduled end of the cycle. Otherwise, omit for remainder of cycle and reduce the dose of lenalidomide by 1 dose level at the start of the next cycle. Omitted doses are not made up. • If Grade 4, discontinue lenalidomide. Remove patient from study.
Desquamating (blistering) rash- any Grade	
 • Discontinue lenalidomide. Remove patient from study.

Table 5: Dose Modifications NOTE: Please consider altering threshold hematologic toxicity criteria for dose modifications depending on specific disease and patient population involved in study, and with consideration given to the Inclusion Criteria and the Instructions for Initiation of a New Cycle. Also consider whether the use of G-CSF is permitted as outlined in the neutropenia row. For combination therapy trials, please consider the following recommendations/issues: 1) it is highly recommended that appropriate dose modifications (holding and reductions as needed) for other drugs in the regimen are incorporated into this table, 2) whether the holding of 1 drug requires other drugs to be held, 3) for drugs with overlapping toxicities (hematologic toxicities, for example) please consider, if appropriate, alternating dose reductions by episode (reduce 1 drug for the first episode and then another drug for the second episode and continuing to alternate which drug is reduced for subsequent reductions as needed, and 4) whether dose modifications for the category "other non-hematologic toxicities \geq grade 3" should be based on attribution (this is recommended).
	
NCI CTC Toxicity Grade	Dose Modification Instructions

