
Neuropathy
 
Grade 3
 
Grade 4
	
 If Grade 3, hold (interrupt) lenalidomide dose. Follow at least weekly. If the toxicity resolves to \leq grade 1 prior to Day 28, restart lenalidomide at next lower dose level and continue through the scheduled end of the cycle. Otherwise, omit for remainder of cycle and reduce the dose of lenalidomide by 1 dose level at the start of the next cycle. Omitted doses are not made up. If Grade 4, discontinue lenalidomide. Remove patient from study.

Venous thrombosis/embolism \geq Grade 3
	
 Hold (interrupt) lenalidomide and start anticoagulation; restart lenalidomide at investigator's discretion (maintain dose level). Omit lenalidomide for remainder of cycle. See Anticoagulation Consideration (Section 5.7.2)

Hyperthyroidism or hypothyroidism
	
 Omit lenalidomide for remainder of cycle, evaluate etiology, and initiate appropriate therapy. Resume lenalidomide at the same dose for 1st occurrence Reduce dose of lenalidomide with 2nd occurrence See Instructions for Initiation of a New Cycle

other non-hematologic toxicity \geq Grade 3
	
 Hold (interrupt) lenalidomide dose. Follow at least weekly. If the toxicity resolves to \leq grade 2 prior to Day 28, restart lenalidomide and continue through the scheduled end of the cycle. Otherwise, omit for remainder of cycle. Omitted doses are not made up. For toxicity attributed to lenalidomide, reduce the lenalidomide dose by 1 dose level when restarting lenalidomide.

Table 6: Dose Interruption/Modification Guidelines for Everolimus

Please note that in case of hematological toxicity, Everolimus dose reduction should be considered only if the dose reduction for lenalidomide has been effected as per Table 5 above and found to be ineffective or insufficient to allow the patient to safely resume therapy per protocol guidelines

Toxicity	Actions

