
Non-hematological toxicity
 
Grade 2 (except pneumonitis – refer to Table 3-2)
 
Grade 3 (except hyperlipidemia*) (except pneumonitis – refer to Table 3-2)
 
Grade 4
	
If the toxicity is tolerable to the patient, maintain the same dose. If the toxicity is intolerable to patient, interrupt RAD001 until recovery to grade ≤ 1. Then reintroduce RAD001 at same dose. If event returns to grade 2, then interrupt RAD001 until recovery to grade ≤ 1. Then reintroduce RAD001 at the lower dose level.
 
Interrupt RAD001 until recovery to grade ≤ 1. Then reintroduce RAD001 at the lower dose level. For pneumonitis consider the use of a short course of corticosteroids.
 
Discontinue RAD001.

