5.7.5 Known Undesirable Side Effects of RAD001

Overall, the most frequent adverse effects suspected to be related to RAD001 have been stomatitis, rash, anemia, fatigue, asthenia, diarrhea, anorexia, nausea, hypercholesterolemia, mucosal inflammation, vomiting, hypertriglyceridemia, cough, peripheral edema, dry skin, epistaxis, pruritus and dyspnea. The most common Grade 3 or 4 adverse reactions suspected to be related to treatment were anemia, infections, hyperglycemia, stomatitis, fatigue, lymphopenia, hypercholesterolemia, pneumonitis, and elevated gamma-glutamyltransferase concentrations.

The principal DLT in Phase 1 trials has been Grade 3 stomatitis. For guidance on management of stomatitis refer to Section 5.7.6.

Hyperlipidemia was reported as a serious adverse reaction. It is a recognized side-effect of rapamycins. Use of lipid-lowering drugs should be associated with dietary recommendations. Monitoring of blood lipid levels requires patients to be fasting so that this aspect must be verified when interpreting results. For guidance on management of hyperlipidemia refer to Section 5.7.7.

Hyperglycemia was reported as a serious adverse reaction. Similarly, the fasting state of patients should be verified when interpreting results. For guidance on management of hyperglycemia refer to Section 5.7.7.

Pneumonitis is a recognized adverse effect of rapamycins (sirolimus, temsirolimus, and everolimus). Numerous case reports in the literature suggest that rapamycin-associated pneumonitis is relatively unaggressive, limited in extent, and reversible upon drug discontinuation. The term ‘pneumonitis’ is used here to describe non-infectious, non-malignant infiltration in the lungs which is evident radiologically. More precise diagnosis should follow histocytological examination following lung biopsy, generally during bronchoscopy which may or may not be symptomatic. Advice on the management of pneumonitis has been provided in Table 7.

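### For a Grade 3 rash attributed mainly to everolimus, section 5.7.3 lowers everolimus only, the Table 5 rash row lowers lenalidomide, and nothing says which prevails

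*Combined protocol and SAP*

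**What the plan says.** Four parts of protocol section 5.7 bear on a Grade 3 non-blistering rash.

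- **5.7.3, text before the tables.** Both drugs are held during an interruption for toxicity. On resumption: "In the case of non-hematological toxicity, dose reduction will be limited to the drug with the highest likelihood of attribution". If attribution is equal or cannot be made, both drugs are lowered.
- **5.7.2, new cycle.** If dosing was omitted for the rest of the previous cycle, or the new cycle is delayed by new toxicity, the "new cycle will be started with a one-level dose reduction of the drug to which the toxicity was attributed".
- **Table 5, Grade 3 non-blistering rash.** If the rash resolves in time, "restart lenalidomide at next lower dose level and continue through the scheduled end of the cycle". If it does not: "Otherwise, omit for remainder of cycle and reduce the dose of lenalidomide by 1 dose level at the start of the next cycle". Neither branch mentions attribution. The Grade 3 neuropathy row is worded the same way.
- **Table 6, Grade 3 non-hematologic toxicity.** Everolimus is interrupted until recovery. "Then reintroduce RAD001 at the lower dose level. For pneumonitis consider the use of a short course of corticosteroids". This row has no attribution wording either.

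The Table 5 row for other non-hematologic toxicity of Grade 3 or higher does make the lenalidomide reduction depend on attribution to lenalidomide. The only stated order between the two drugs, in 5.7.3 and in the lead-in to Table 6, is for hematologic toxicity.

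Rash is listed for both drugs. For everolimus, 5.7.5 says "the most frequent adverse effects suspected to be related to RAD001 have been stomatitis, rash, anemia, fatigue". The lenalidomide list in 3.3.1 includes "vomiting and diarrhea, dehydration, rash, itching, infections, sepsis, pneumonia, UTI, Upper respiratory infection".

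**The concern.** Two rules in the same section can give one patient two different doses. The 5.7.3 text bars a lenalidomide reduction when everolimus is the likelier cause; the rash row orders it. The second branch of the row and the 5.7.2 rule share a trigger, dosing omitted for the rest of the cycle, but the row names lenalidomide whatever the attribution.

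The missing condition cannot safely be read into the rash row, because another row of the same table states it. An investigator who holds that the specific row overrides the general text would lower lenalidomide. One who takes the 5.7.3 limit at its word would not. At stake is an individual patient's dose: lenalidomide given up for a toxicity attributed to the other drug and, on the narrowest reading, the implicated everolimus dose left unchanged.

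**Working it through.** The plan states no figure on this point. The check compares the instructions, then sizes how often they could diverge.

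**Where the instructions diverge.** Outcome for a Grade 3 non-blistering rash, by attribution:

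| Attribution | 5.7.3 text | Table 5 rash row | Same lenalidomide step? |
|---|---|---|---|
| Mainly lenalidomide | lower lenalidomide | lower lenalidomide | yes |
| Equal or unclear | lower both | lower lenalidomide (silent on everolimus) | yes |
| Mainly everolimus | lower everolimus only | lower lenalidomide | no |

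Only the last line is a direct conflict over lenalidomide.

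**Worked dose.** Take level 5 of Table 1, lenalidomide/everolimus 25/10 mg, as an illustration. It is the only level with 10 mg everolimus. One step down is 25 to 20 mg for lenalidomide (Table 3). For everolimus it is 10 mg to 5 mg daily, which is how I read Table 4. With the rash attributed mainly to everolimus:

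- 5.7.3 text: 25/5.
- Both tables applied: 20/5.
- Rash row alone: 20/10.

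Over a full 28-day cycle:

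- One lenalidomide step is 25 × 28 = 700 mg down to 20 × 28 = 560 mg, and 560/700 = 80% of assigned.
- One everolimus step is 10 × 28 = 280 mg down to 5 × 28 = 140 mg, or 50%.

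**How often.** Inputs:

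- Patients still to be treated under these rules: 15 + 9 = 24 in the two expansion cohorts. Section 10.6 says the escalation needed only 21 patients.
- Rate p of Grade 3 rash attributed mainly to everolimus: not given. Section 3.3.2 lists the most common Grade 3/4 reactions at 3% incidence or more among 274 everolimus patients, and rash is not there. Section 5.7.5 lists the most common related Grade 3 or 4 reactions, and rash is not there either. I therefore assume p from 1% to 3%.

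Expected number = 24p. Chance of at least one = 1 − (1 − p)^24.

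| Assumed p | Expected of 24 | Chance of at least one |
|---|---|---|
| 1% | 24 × 0.01 = 0.24 | 1 − 0.99^24 = 0.21 |
| 3% | 24 × 0.03 = 0.72 | 1 − 0.97^24 = 0.52 |

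**What it does not touch.** Sections 5.7.1 and 5.7.3 leave cohort escalation to Table 1. DLTs are assessed in cycle 1 only, and Grade 3 non-hematologic toxicity is on the DLT list whichever drug is lowered afterwards. The exposure summary in 10.2 is descriptive, and 5.6.2 requires all dose changes to be recorded.

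**The case against.** The best defence is that a workable reading exists. The 5.7.3 text is written for this combination, introduces both tables and is exclusive in its wording; 5.7.2 agrees with it. An investigator could choose the drug by 5.7.3 and then use that drug's table. This carries weight and keeps the point small. It does not remove it: the document never states that order, and the attribution condition in the other non-hematologic row of Table 5 invites the opposite inference for rash.

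Several stronger readings are tempting, and the documents do not support them.

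- *The conflict will be frequent.* The any-grade list in 5.7.5 could suggest rates of 5% or 10%. Absence from both Grade 3/4 lists points lower. The event must also be judged mainly due to everolimus in a patient who is taking lenalidomide, for which rash is listed too.
- *Patients will stay on the everolimus dose that caused the rash.* The 20/10 outcome requires setting aside both the 5.7.3 text and the Table 6 Grade 3 row. The likelier divergence is 25/5 against 20/5, one extra lenalidomide step in the cautious direction.
- *Neuropathy is an equal problem.* Its row also says "reduce the dose of lenalidomide by 1 dose level at the start of the next cycle", but the available text of 3.3.2 and 5.7.5 does not list neuropathy as an everolimus effect. It is a drafting parallel and not a practical case.
- *The size should be quoted across all dose levels.* Expansion patients are treated at one recommended dose, so a spread over the whole of Table 1 says little about them.
- *Table 6 contradicts 5.7.3 as well.* Section 5.7.5 describes Table 6 as guidance for suspected RAD001 toxicity, though for single-agent use. That is an ambiguity, not a contradiction.

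**Conclusion.** The inconsistency is real and narrow. For a Grade 3 non-blistering rash attributed mainly to everolimus, 5.7.3 and, where its trigger applies, 5.7.2 lower everolimus only. The Table 5 row lowers lenalidomide, with no stated precedence. The consequence for such a patient is one unplanned lenalidomide step and, only if the row is followed in isolation, an unchanged everolimus dose.

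Under the assumed 1% to 3%, fewer than one of the 24 expansion patients is expected to meet the conflict, and the chance of at least one runs from about one in five to about one in two. The 3% end assumes that the list in 3.3.2 is complete and that single-agent experience carries over to the combination. The 25/10 mg example is illustrative and rests on my reading of Table 4.

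A reader might infer that the MTD or recommended dose is at risk. It is not, and no endpoint changes. This is a minor patient-dosing correction, worth making because the plan's own rules disagree and the remedy is simple.

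**What to change.** 1. Add one sentence to 5.7.3 stating that its attribution rule governs non-hematologic dose reductions in both Table 5 and Table 6.
2. In the Table 5 Grade 3 non-blistering rash row, add to the dose-reduction step: *if attributed to lenalidomide, or if attribution is equal or unclear*. Add the same condition to the Grade 3 neuropathy row for consistency.
3. Keep the hold of both drugs during the interruption as it stands. Only the reduction on resumption becomes conditional.

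The single-agent sentence about Table 6 in 5.7.5 need not be reworded, since the new sentence in 5.7.3 settles the matter.

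The cost is a wording amendment: one sentence and one condition in two rows. No new data are needed, because section 6.3 already asks for each adverse event's relationship to the study drug or drugs. Sample size and analyses do not change.

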5.7.4 Monitoring of RAD001 suspected toxicities

Patients whose treatment is interrupted or permanently discontinued due to an adverse event or abnormal laboratory value suspected to be related to RAD001 must be followed at least weekly until the adverse event or abnormal laboratory resolves or returns to grade 1. If a patient requires a dose delay of > 21 days from the intended day of the next scheduled dose, then the patient must be discontinued from the study.

5.7.5 Known Undesirable Side Effects of RAD001

Overall, the most frequent adverse effects suspected to be related to RAD001 have been stomatitis, rash, anemia, fatigue, asthenia, diarrhea, anorexia, nausea, hypercholesterolemia, mucosal inflammation, vomiting, hypertriglyceridemia, cough, peripheral edema, dry skin, epistaxis, pruritus and dyspnea. The most common Grade 3 or 4 adverse reactions suspected to be related to treatment were anemia, infections, hyperglycemia, stomatitis, fatigue, lymphopenia, hypercholesterolemia, pneumonitis, and elevated gamma-glutamyltransferase concentrations.

The principal DLT in Phase 1 trials has been Grade 3 stomatitis. For guidance on management of stomatitis refer to Section 5.7.6.

Hyperlipidemia was reported as a serious adverse reaction. It is a recognized side-effect of rapamycins. Use of lipid-lowering drugs should be associated with dietary recommendations. Monitoring of blood lipid levels requires patients to be fasting so that this aspect must be verified when interpreting results. For guidance on management of hyperlipidemia refer to Section 5.7.7.

Hyperglycemia was reported as a serious adverse reaction. Similarly, the fasting state of patients should be verified when interpreting results. For guidance on management of hyperglycemia refer to Section 5.7.7.

Pneumonitis is a recognized adverse effect of rapamycins (sirolimus, temsirolimus, and everolimus). Numerous case reports in the literature suggest that rapamycin-associated pneumonitis is relatively unaggressive, limited in extent, and reversible upon drug discontinuation. The term ‘pneumonitis’ is used here to describe non-infectious, non-malignant infiltration in the lungs which is evident radiologically. More precise diagnosis should follow histocytological examination following lung biopsy, generally during bronchoscopy which may or may not be symptomatic. Advice on the management of pneumonitis has been provided in Table 7.

Discrete, reversible changes in liver enzymes have been found to occur in numerous patients during treatment with RAD001 in oncology clinical studies, and in a study in rheumatoid arthritis. In oncology studies, these changes may be evident only in patients without severe underlying morbidity. The increase in transaminase's (AST and ALT) generally appears after 4 weeks of treatment. In all but a few cases it does not exceed Grade 1 ($\leq 2.5 \times \text{ULN}$). Similarly, mild increases in alkaline phosphatases can coexist. Spontaneous corrections or intermittent correction with continued treatment can occur. Serum bilirubin is not increased. In studies of patients with advanced cancers, clinically relevant changes in liver enzymes have been invariably associated with the presence of liver metastases and/or progression of the underlying cancer.

Renal failure has been reported in five suspected cases to date. One patient with no alternative explanation made a complete recovery following study drug adjustment and no treatment/therapy for the event. The rest of the patients had concurrent morbidities, which might have contributed to the reported events.

Hypophosphatemia, hypomagnesemia, hyponatremia and hypocalcemia have been reported as serious adverse reactions. Electrolytes should be monitored in patients treated with RAD001.

Table 6 provides general recommendations for the management of patients, with suspected drug toxicities while on treatment with RAD001 as single-agent therapy.

More detailed information regarding RAD001 reported suspected toxicities and individual cases is provided in the [Investigator's Brochure].

5.7.6 Management of stomatitis/oral mucositis/mouth ulcers

Stomatitis/oral mucositis/mouth ulcers due to RAD001 should be treated using local supportive care. Please note that investigators in earlier trials have described the oral toxicities associated with RAD001 as mouth ulcers, rather than mucositis or stomatitis. If your examination reveals mouth ulcers rather than a more general inflammation of the mouth, please classify the adverse event as such. Please follow the paradigm below for treatment of stomatitis/oral mucositis/mouth ulcers:

1. For mild toxicity (Grade 1), use conservative measures such as **non-alcoholic mouth wash or salt water (0.9%) mouth wash** several times a day until resolution.
2. For more severe toxicity (Grade 2 in which case patients have pain but are able to maintain adequate oral alimentation, or Grade 3 in which case patients cannot maintain adequate oral alimentation), the suggested treatments are **topical analgesic mouth treatments (i.e., local anesthetics such as benzocaine, butyl aminobenzoate, tetracaine hydrochloride, menthol, or phenol)** with or without **topical corticosteroids**, such as triamcinolone oral paste 0.1% (Kenalog in Orabase[®]).
3. Agents containing hydrogen peroxide, iodine, and thyme derivatives may tend to worsen mouth ulcers. It is preferable to avoid these agents.
4. Antifungal agents must be avoided unless a fungal infection is diagnosed. In particular, systemic imidazole antifungal agents (ketoconazole, fluconazole, itraconazole, etc.) should be avoided in all patients due to their strong inhibition of RAD001 metabolism, thereby leading to higher RAD001 exposures. Therefore, topical antifungal agents are preferred if an infection is diagnosed. Similarly, antiviral agents such as acyclovir should be avoided unless a viral infection is diagnosed.

Note: Stomatitis/oral mucositis should be appropriately graded using the functional grading given on the NCI-CTC for adverse events, version 3.0.

